7.3.2 Univariate analysis

Univariate analyses will be performed for all variables of interest. These will be carried out by comparing the changes from baseline using signed rank tests for continuous variables and McNemar's test for categorical variables.

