- Initiation of PAH therapy (prostacyclin analogues or receptor agonists, endothelin-1 receptor antagonists, phosphodiesterase-5 inhibitors, soluble guanylate cyclase stimulators) within three months of enrollment; the dose must be stable for at least 3 months prior to Baseline Visit. PAH therapy which is stopped and then restarted or has dose changes which are not related to initiation and uptitration will be allowed within 3 months prior to the Baseline Visit.
- Hormone therapy.
- Use of warfarin or other anticoagulant (use of aspirin is permitted).
- Platelet count <100,000.
- Renal failure (creatinine \geq 2.0).
- Child-Pugh Class C cirrhosis.
- Current or recent (< 6 months) chronic heavy alcohol consumption.
- Current use of another investigational drug (non-FDA approved) for PAH.

ENDPOINTS:

- Changes in right ventricular systolic pressure, right ventricular fractional area, stroke volume index and tricuspid annular plane systolic excursion
- Changes in six-minute walk distance
- Changes in plasma NT-proBNP and estradiol levels
- Assess safety and side effects associated with fulvestrant administration in subjects with pulmonary arterial hypertension

STUDY OBSERVATIONS:

- Subjects will be evaluated in person at screening, baseline, two weeks, four weeks, eight weeks and nine weeks.
- Subjects will have telephone follow-up at week twelve.
- Laboratory tests including a complete blood count, hepatic function panel, follicle-stimulating hormone, coagulation studies (PT/INR) will be performed at the screening visit.
- Research laboratories such as estradiol (E2) and NT-proBNP levels will be evaluated at baseline and repeated after nine weeks of fulvestrant administration.
- Subjects will have six minute walk testing at baseline and week nine.
- Subjects will have a transthoracic echocardiogram at screening or baseline and week nine.

SAMPLE SIZE AND POWER:

A total of 5 subjects will be enrolled to receive fulvestrant at baseline, two weeks, four weeks, and eight weeks. Formal power calculations were not performed as this study is intended to show feasibility and for hypothesis-generation.

DATA ANALYSIS:

The study endpoints will be evaluated using summary statistics and graphical tools. Univariate analysis will be performed for all variables of interest. These will be carried out by comparing the changes from baseline using signed rank tests for continuous variables and McNemar's test for categorical variables.

Brief Table of Contents

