7.3 Statistical procedures

7.3.1 Data analysis

Prior to the formal analysis, the distributions of the key variables to be used in the analyses will be examined using summary statistics and graphical tools.

Outcomes of interest will be evaluated with a per-protocol analysis. Subjects who are not compliant or stop the treatment portion of the study will be replaced (although their data will also be considered in secondary analyses). Outcomes include estradiol levels, TAPSE and other echocardiographic measures, 6MWD, plasma NT-proBNP level, and other variables as well as safety and side effects.

These measures will be assessed both at baseline and nine weeks. Summary statistics will be produced with both the repeated measures as well as the calculated differences from the baseline. We will summarize demographics and other predictors of clinical status. Continuous variables will be summarized by the mean, median, standard deviation, and range, as appropriate. We will use contingency tables for discrete and dichotomous variables.

Hypothesis testing will use two-sided $\alpha= 0.05$. All statistical analyses will be performed using SAS and R.

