7.3.3 Missing data and dropouts

Patients who drop out from treatment or assessment plan will be replaced.

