7.4 Sample size and power calculations

Formal power calculations have not been performed. This study is intended for hypothesis generation and to show feasibility.

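### With five subjects, exact signed-rank and McNemar tests cannot give a two-sided p below 0.0625, so the plan's 0.05 rule cannot be met, and the plan does not name the test version

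*Combined protocol and SAP*

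**What the plan says.** The Protocol Summary (Sample size and power) sets the size: "A total of 5 subjects will be enrolled to receive fulvestrant at baseline, two weeks, four weeks, and eight weeks". Section 7.3.1 makes the outcome analysis per-protocol and replaces subjects who are non-compliant or stop treatment. Section 7.3.3 repeats the replacement rule: "Patients who drop out from treatment or assessment plan will be replaced". The main paired comparison of baseline with week 9 therefore has n = 5.

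On testing, section 7.3.1 says "Hypothesis testing will use two-sided" alpha of 0.05. Section 7.3.2 and the Summary name the method for all variables of interest: "comparing the changes from baseline using signed rank tests for continuous variables and McNemar's test for categorical variables". On software, the plan says only "All statistical analyses will be performed using SAS and R". No procedure or option is given, and nothing says whether the tests are exact, asymptotic or continuity-corrected.

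The plan also has a descriptive strand. Section 7.3.1 says "Summary statistics will be produced with both the repeated measures as well as the calculated differences from the baseline", and the Summary says "The study endpoints will be evaluated using summary statistics and graphical tools". Section 7.4 reports no power calculation and gives the purpose: "This study is intended for hypothesis generation and to show feasibility".

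**The concern.** Both named tests rest on the direction of change within each subject. Five subjects give only 32 patterns of direction, so an exact p-value moves in coarse steps and has a floor. If that floor lies above 0.05, the only testing rule in the plan cannot be satisfied by a valid test, whatever the drug does.

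Two misreadings could follow. A result in which all five subjects move the same way, the strongest result these tests can give, could be reported as not significant. Conversely, a printed p below 0.05 could arise from the choice of test version or from tied values and be read as stronger evidence.

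**Working it through.** **Inputs.** n = 5 (Protocol Summary; sections 7.3.1 and 7.3.3); two-sided alpha 0.05 (7.3.1); signed rank and McNemar (7.3.2); SAS and R (7.3.1). The plan gives no power or sample-size figure to reproduce.

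**Step 1: exact floor.** Under the null each non-zero change is equally likely to be up or down, so there are 2^n equally likely sign patterns. The two most extreme are all up and all down, so the smallest two-sided p is 2/2^n. Exact McNemar with all n pairs discordant in one direction gives the same value, 2 × 0.5^n.

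| Non-zero changes or discordant pairs | Smallest exact p | Next signed-rank p |
|---|---|---|
| 4 | 2/16 = 0.125 | 0.25 |
| 5 | 2/32 = 0.0625 | 0.125 |
| 6 | 2/64 = 0.03125 | 0.0625 |

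At n = 5 nothing lies at or below 0.05, so the rejection rate is 0 under the null and under any alternative. One zero change or one concordant pair moves the floor to 0.125.

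**Step 2: large-sample versions, signed rank.** With all five changes positive, W = 15, the null mean is 5×6/4 = 7.5 and the variance is 5×6×11/24 = 13.75 (SD 3.708).
- Uncorrected: z = 7.5/3.708 = 2.02, p = 0.043.
- Continuity-corrected: z = 7.0/3.708 = 1.89, p = 0.059.
- Next result, W = 14, uncorrected: z = 6.5/3.708 = 1.75, p = 0.080.

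The uncorrected test thus rejects only on the two extreme patterns, whose null probability is 0.0625, not 0.05.

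**Step 3: large-sample versions, McNemar.** Uncorrected chi-square is (b−c)²/(b+c); corrected is (|b−c|−1)²/(b+c).

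| Discordant split | Uncorrected | Corrected | Exact |
|---|---|---|---|
| 5–0 | 25/5 = 5, p = 0.025 | 16/5 = 3.2, p = 0.074 | 0.0625 |
| 4–0 | 16/4 = 4, p = 0.046 | 9/4 = 2.25, p = 0.134 | 0.125 |

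Mid-p for 5–0 is 0.031, another version that prints below 0.05.

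Given five or four discordant pairs, the uncorrected test rejects under the null with probability 0.0625 or 0.125. Averaged over all five pairs, with discordance probability d, its null rejection rate is 0.0625d⁵ + 0.125×5d⁴(1−d). This is 0.021 at d = 0.5, passes 0.05 at about d = 0.67, and peaks at 0.078.

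**Step 4: ties in R.** The default signed-rank function (R 4.3.3) gives 0.0625 for five distinct same-direction changes. With ties it switches to the corrected approximation, with the variance reduced by the sum of (t³−t)/48 over tied groups of size t:
- two tied: variance 13.75 − 0.125 = 13.625, p = 0.058;
- four tied: 13.75 − 1.25 = 12.5, p = 0.048;
- all five tied: 13.75 − 2.5 = 11.25, p = 0.037.

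With all five changes equal, the null probability that they share a direction is still 0.0625.

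**Step 5: how much signal a p of 0.0625 can carry.** Assume normal changes with true mean change of k SD. The probability that all five move the same way is Φ(k)⁵ + Φ(−k)⁵: 42% for k = 1, 71% for k = 1.5 and 89% for k = 2. A clear effect would often show as unanimity, and the 0.05 cutoff would still call it negative.

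**Step 6: McNemar and WHO class.** McNemar's usual form needs two levels. Section 6.1.6 describes four ordered classes, with Class IV excluded at entry (3.2.2), and no split is defined. On a three-level table with two subjects moving from II to I and three from III to II, R's default McNemar function returns no usable p-value.

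**The case against.** The strongest reply is that little depends on this. The study is for feasibility and hypothesis generation, no success rule uses alpha, and the Summary puts summary statistics and graphics first. Mean, median, SD, range and contingency tables are already planned, so much of the remedy is in place. That is right, and it limits the harm to reporting. It does not rescue the 0.05 rule, which remains a stated commitment that valid tests cannot meet.

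A second reply is that misleading p-values need particular circumstances. R's defaults give 0.0625 for five distinct changes and 0.074 for McNemar 5–0. With ties, the corrected signed-rank approximation falls below 0.05 only when at least four absolute changes are tied, which is unlikely for NT-proBNP, estradiol or walk distance. This stands for R's defaults. SAS, the other named package, was not examined, and the plan binds the analyst to no version.

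Third, the 0.0625 and 0.125 rates for McNemar are conditional on the number of discordant pairs, and the unconditional rate can be well below 0.05. That is correct. However, conditioning is standard for this test, and the unconditional maximum of 0.078 still exceeds the nominal level.

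Fourth, section 7.3.1 lets replaced subjects' data enter secondary analyses. With six usable pairs the exact floor is 0.03125. That also stands: the point concerns the five-subject per-protocol analysis, which is the main one.

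**Conclusion.** The concern holds. In the five-subject per-protocol analysis, exact signed-rank and exact McNemar tests have a smallest two-sided p of 0.0625 (0.125 with four informative pairs), so power at 0.05 is zero for every outcome. This is an enumeration and needs no assumption about effect size or distribution beyond the null symmetry of the tests themselves. Versions that print below 0.05 do so by understating the null probability of the observed pattern: 0.043 and 0.025 against 0.0625, and 0.046 against 0.125, the McNemar figures being conditional on the discordant pairs.

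The consequence is moderate. It concerns how tests are reported and read, not the data collected, the planned summaries or any decision. It should be corrected before analysis. The undefined split for WHO class is a smaller specification gap alongside it; the conclusion does not depend on it.

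**What to change.** In sections 7.3.1 and 7.3.2 and the Summary:

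- Remove the 0.05 testing rule and make the change summaries already planned the main analysis.
- Add each subject's change and an interval for each outcome. The median with minimum to maximum has coverage 1 − 2/32 = 93.75% at n = 5. Optionally add the mean with a 95% t-interval, half-width 2.776/√5 = 1.24 SD.
- Show WHO class as a baseline by week 9 shift table.
- If p-values are kept, specify exact versions of both tests and state that the smallest attainable value is 0.0625. State also that p above 0.05 will not be read as no effect and that no significance claim will be made.

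The cost is wording only; no data, visits or subjects are added. The plan gives up nominal significance testing. The optional t-interval assumes approximate normality, which five values cannot check, and it should not be used as a substitute 0.05-level test.

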7.3.3 Missing data and dropouts

Patients who drop out from treatment or assessment plan will be replaced.

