1.1 Definition and characterization of PAH

Pulmonary arterial hypertension (PAH) is defined by a mean pulmonary artery pressure > 25 mm Hg, a pulmonary vascular resistance > 3 WU, and a normal pulmonary capillary wedge pressure. Endothelial thickening, smooth muscle hypertrophy, and *in situ* thrombosis are present in small pulmonary arteries, however the disease mechanism is unknown. The three year survival is only 60%.

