9.5 Other events

We will not discontinue study drug for clinical events not thought to be serious drug-related AEs. For example, a hospitalization for clinical worsening will not result in cessation of trial participation. Such events could result in missing data for primary and secondary endpoints, comprising the integrity of the analysis. As the trial does not prohibit any therapies which is the standard of care in PAH, there is no ethical or safety reason to stop trial participation under such circumstances. Even if subjects are withdrawn from the study drug outcome assessments will continue. Subjects who are not compliant or stop the treatment portion of the study will be replaced.

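### Section 7.3.3 has a wider replacement trigger than 7.3.1 and 9.5, and as the only missing-data rule it lets a dosed subject lost to death or worsening be replaced by a completer in the main summary

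*Combined protocol and SAP*

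**What the plan says.** The Protocol Summary, under sample size, states: "A total of 5 subjects will be enrolled to receive fulvestrant at baseline, two weeks, four weeks, and eight weeks". Section 7.4 adds: "Formal power calculations have not been performed". It describes the aim as generating hypotheses and showing feasibility.

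Three sections govern replacement:

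- Section 7.3.1 sets the analysis, "Outcomes of interest will be evaluated with a per-protocol analysis", and then the rule: "Subjects who are not compliant or stop the treatment portion of the study will be replaced". A clause in brackets keeps what was recorded on these subjects for use in secondary analyses.
- Section 9.5 repeats the rule without the clause about secondary analyses. It also says that a hospitalization for worsening does not end participation, because "Such events could result in missing data for primary and secondary endpoints".
- Section 7.3.3, which is one sentence long, says: "Patients who drop out from treatment or assessment plan will be replaced".

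The last dose is on day 56 (section 4.1). Blood sampling, echocardiography and the walk test are done at baseline and once afterwards, at week 9 (section 7.1). No section says how death, or being too ill to be tested, enters the outcome analysis.

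**The concern.** The trigger in 7.3.3 is wider than the one in 7.3.1 and 9.5, because only 7.3.3 adds loss from assessment. That matters because 7.3.3 is the whole missing-data method. With a single post-baseline efficacy visit, a woman can receive every dose and still have no outcome value.

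If her data are missing because she died or deteriorated, replacement selects on outcome: an unfavourable result leaves the main summary and someone well enough to complete takes the place. With no control arm, nothing offsets that selection, and the reported changes in walk distance, right ventricular function and NT-proBNP lean toward benefit. Feasibility is also a stated purpose, so failure to reach week 9 is itself a finding, and it would drop out of the main summary.

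The secondary-analysis clause in 7.3.1 does not repair this, since a measure never taken at week 9 leaves no change to analyse.

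**Working it through.** **1. The rules side by side**

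| Section | Stops treatment | Not compliant | Leaves assessment plan | Data kept for secondary analyses |
|---|---|---|---|---|
| 7.3.1 | replaced | replaced | not named | yes |
| 9.5 | replaced | replaced | not named | not stated |
| 7.3.3 | replaced | not named | replaced | not stated |

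The plan has no sample-size calculation to reproduce; 5 is simply stated.

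**2. How often death alone could trigger this**

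Input: section 1.1, "The three year survival is only 60"%. Assumption: constant hazard.

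Hazard h = −ln(0.60)/3 = 0.1703 per year. Risk over d days: q = 1 − exp(−h·d/365.25). Chance of at least one death among 5: 1 − (1 − q)^5.

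| Interval | d | q | At least one of 5 |
|---|---|---|---|
| Day 56 to day 63 (fully treated, as scheduled) | 7 | 0.33% | 1.6% |
| Day 53 to day 70 (widest gap the windows allow: 56 − 3 to 63 + 7) | 17 | 0.79% | 3.9% |
| All nine weeks | 63 | 2.9% | 13.7% |

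Excluding WHO class IV should lower these figures.

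Non-fatal worsening adds to them, but the documents give no rate for it. If the total loss per subject is assumed to be 2%, 5%, 10% or 20%, the chance of at least one loss among 5 is 1 − 0.98^5 = 9.6%, 1 − 0.95^5 = 22.6%, 1 − 0.90^5 = 41.0% or 1 − 0.80^5 = 67.2%. This range is illustrative only.

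**3. What one such subject does to the result**

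One subject is 1/5 = 20% of the sample. Suppose the other four improve. The exact two-sided signed-rank p is twice the number of sign patterns at least as extreme, divided by 2^n.

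- Replaced by an improver, n = 5, all positive: 2 × 1/32 = 0.0625.
- Simply missing, n = 4, all positive: 2 × 1/16 = 0.125.
- Kept and ranked worst, n = 5: the negative rank sum is 5, and 10 of 32 patterns have a sum of 5 or less, so 2 × 10/32 = 0.625.
- Kept and ranked worst with one more improver added, n = 6: the negative rank sum is 6, and 14 of 64 patterns have a sum of 6 or less, so 2 × 14/64 = 0.4375.

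The smallest attainable p with n = 5 is 0.0625, above the two-sided 0.05 of section 7.3.1.

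**The case against.** The strongest reply is that the protocol never says what the concern fears. No section calls death, hospitalization or inability to walk a drop-out. Section 9.5 keeps a hospitalized subject in the trial, section 9.6.5 continues scheduled assessments after treatment stops, and section 5.1.8 asks for the week-9 procedures at early withdrawal. A woman who cannot do the walk test can still give blood and have an echocardiogram at Visit 5. The event would also be recorded elsewhere: safety covers all subjects (7.7), and the number completing each visit is reported (7.2).

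Most of this stands, and it rules out several stronger readings that a reader might infer:

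- *That 7.3.3 expressly replaces a woman who dies or is too ill.* It does not. That is a fair inference from the only missing-data rule, not a stated provision.
- *That 7.3.1 clearly keeps her.* Sections 5.3 and 9.6.5 speak of complying with study visits, so *not compliant* may already cover a voluntarily missed assessment. It does not naturally cover death or illness. In any case, a subject without a week-9 value contributes no change to a per-protocol analysis.
- *That 13.7% is the risk for a fully treated subject.* That figure spans all nine weeks. Most of those deaths would come before the fourth dose, where treatment has also stopped and 7.3.1 arguably replaces her too.
- *That replacement moves p from 0.625 to 0.0625.* The 0.625 needs a worst-rank convention that the plan does not contain. Against simple missingness the contrast is 0.125 with 0.0625.

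What the reply does not answer is the main efficacy summary. Safety tables, visit counts and secondary analyses record the loss, but none of them corrects that summary.

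**Conclusion.** The three sections disagree, the key terms are undefined, and the widest version is the operative missing-data rule. It permits selection on outcome in the main per-protocol summary, with bias toward apparent benefit.

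The case of a fully treated subject who dies before week 9 is rare: 1.6%, or 3.9% at the widest windows. Across all dosed subjects and all nine weeks the figure is 13.7%. These figures rest on a constant hazard and count death only. The direction of the bias assumes that the data are missing because of clinical status.

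A reader might infer that the false-positive rate is inflated. The documents do not support that at the planned size, because 5 subjects cannot reach 0.05 and the study is declared hypothesis-generating. The harm is to the estimated changes and to the feasibility message. The point should be settled before enrolment, but it does not put the design itself in question.

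**What to change.** Reconcile 7.3.1, 7.3.3 and 9.5 into one replacement rule:

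- Define *drop out* and *not compliant*, and say whether each refers to dosing, visits or both.
- Keep in the main outcome tables any subject who has received at least one dose and whose week-9 data are missing because of death, clinical worsening or inability to perform a test. Anyone enrolled in addition is added to her and does not take her place.
- Use whatever week-9 measures she can provide.
- Report the number of replacements with reasons, and show results for all dosed subjects beside the per-protocol completers.
- For the clinical-status endpoints only (walk distance, right ventricular function, NT-proBNP), add a worst-rank sensitivity analysis with medians. Do not extend it to estradiol or progenitor cells, where death has no natural worst rank.

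Editing 7.3.3 alone to match 7.3.1 is not enough, because a subject who dies before the fourth dose has stopped treatment and could still be replaced.

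The cost is a few sentences and one extra set of tables, with no new data. If such an event occurs, the summary will be less favourable or less tidy, and the worst-rank convention will need explaining. If a sixth subject brings the number of observed changes to 6, the smallest attainable p falls to 2/64 = 0.03125, so the tests should still be presented as descriptive.

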7.4 Sample size and power calculations

Formal power calculations have not been performed. This study is intended for hypothesis generation and to show feasibility.

7.5 Interim monitoring guidelines

We have not planned for formal interim analyses for efficacy.

7.6 Protocol violations

Serious protocol violations such as discontinuation of experimental treatment unrelated to AEs will be carefully recorded and regularly reviewed by the Principal Investigator at each site and by the lead site. Remedial changes in procedure will be recommended where feasible to reduce the incidence of such violations. The causes and circumstances of all violations will be documented where known for purposes of future secondary analyses and interpretation.

7.7 Safety

All subjects will be assessed for toxicity and included in the safety analysis. This analysis will include summaries of the incidence and grade of toxicities.

Chapter 8. Quality Control

Design strategies and monitoring activities throughout the study will ensure the integrity and high quality of the data. Design strategies training and certification of personnel. The monitoring program includes data queries over the time of the trial.

